6. STUDY PROCEDURES AND GUIDELINES

Study-specific assessments and the study schedule are summarized in [Table 6-1](#). An "X" indicates when the assessments are to be performed.

Due to COVID-19 restrictions/policies/quarantines and to maintain safety of staff at individual sites and for individual subjects, it is acknowledged that strict adherence to [Table 6-1](#) for those procedures requiring direct contact with patients (such as laboratory sampling, physical examination, etc) may not be possible for every timepoint listed. The sites should try to maintain the schedule as closely and as safely as feasible, but temporal divergence for these direct contact procedures will not be considered a protocol deviation.

Hospital discharge may occur at any point. The date and time for the hospital discharge decision should be documented in the study records, as duration of hospitalization is a secondary study endpoint.

For subjects who are discharged before Day 14, assessments through Day 14 may be collected, either through at-home visits by trained medical professional(s), outpatient visits or by telephone follow-up, as feasible depending on the site and subject limitations.

If a subject is discharged before dosing is complete, the discharge plan should include completion of study drug dosing.

Protocol Number: AT-03A-001

Follow-up evaluations will occur at 7 days, 14 days and 49 days after study completion at nominal Day 14, according to the table below.

Additional logistical considerations and clarifications

- It is logistically feasible and acceptable for Screening and Day 1 to occur on the same day, as long as eligibility is confirmed before dosing is initiated. If the Screening and Day 1 visits are on the same day, duplicate assessments and laboratory samples do not need to be collected twice.
- Once subjects are confirmed eligible at Screening, randomization and dosing should be initiated within 24 hrs.

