8.2.5. Safety Endpoints

Safety-related comparisons for the two treatments in this trial will include:

- Proportions of subjects experiencing SAEs
- Proportions of subjects with fatal outcomes
- Proportions of subjects experiencing AEs
 - Overall, and by body system as coded by MedDRA
- Proportions of subjects experiencing drug-attributed AEs
- Proportions of subjects experiencing graded laboratory abnormalities
 - With abnormality grades defined in the referenced DAIDS table
- Proportions of subjects discontinuing study for AEs
- Proportions of subjects discontinuing treatment for AEs

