8.4. Safety and PK Analyses

Safety Analyses

Assessing safety and tolerability of AT-527 at the selected dose will be an important objective of the study.

Protocol Number: AT-03A-001

Proportions of subjects experiencing SAEs, AEs, AEs resulting in treatment discontinuation and graded laboratory abnormalities will be summarized. Treatment-emergent AEs and laboratory abnormalities, defined as post-Baseline new AEs or worsened AEs, or new or worsening laboratory parameters, beginning with or after the first dose of study drug, will be included in the safety analyses. These safety-related observations will be summarized by treatment group, primarily using descriptive statistics, with use of time-to-event sub-analyses when appropriate for comparative time-related analyses of any specific clinically severe findings (e.g. death, SAEs, grade 3-4 AEs, or clinically significant grade 3-4 laboratory abnormalities).

Laboratory, ECG and vital sign data will also be summarized with descriptive statistics.

Descriptive statistics will also be used to summarize demographic variables. Other data to be summarized will include medical history, physical examination findings and concomitant medications.

PK Analyses

Plasma concentrations of study drug and metabolites in sparse samples will be listed with time data and summarized using descriptive statistics, as applicable.

Additional details regarding safety and PK analyses will be provided in the SAP.

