**Table B: Analysis Visit Windows**

Scheduled Visit	Target Day of the Visit	Analysis Visit Window
Analysis visit windows for safety labs and SARS-CoV-2 Test		
Baseline	Day 1	Day -1 or Day 1/before 1 st dose
Day 2	Day 2	Day 2 to Day 3
Day 5	Day 5	Day 4 to Day 6
Day 8	Day 8	Day 7 to Day 9
Day 10	Day 10	Day 10 to Day 11
Day 12	Day 12	Day 12 to Day 13
Day 14	Day 14	Day 14 to Day 18
Day 21	Day 21	Day 19 to Day 25
Day 28	Day 28	Day 26 to Day 46
Day 63	Day 63	Day 47 to Day 79

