#### 17.1. ADVERSE EVENTS

- Prior AEs are defined as any AE that started or worsened in severity on or after the date of signed informed consent but before the first dose of study drug.

Document: \[REDACTED]\net\enterprise\Apps\sasdata\SASb\SAS\Atea\_Pharmaceuticals\AT-527\SAZ\A63631\Biostatistics\Documentation\SAP\AT-03A-001\_V1.0\_COVID\_SAP\_PA7.doc  
Author: \[REDACTED]

Version Number: V1.0  
Version Date: 15Apr2021

Template No.: CS\_TP\_BS016 Revision 6

Reference: CS\_WI\_BS005

Effective Date: 02Dec2019

Copyright © 2009, 2010, 2012, 2016, 2018, 2019 \[REDACTED] All rights reserved. The contents of this document are confidential and proprietary to \[REDACTED] Holdings Inc. and its subsidiaries. Unauthorized use, disclosure or reproduction is strictly prohibited.

- Treatment emergent AEs (TEAEs) are defined as any AE that started or worsened in severity on or after the first dose of study drug but no later than 28 days after the last dose of study drug. Events considered as possibly related to study drug that occur in follow-up more than 28 days after last study drug will also be considered TEAE.

See APPENDIX 1 for handling of partial dates for AEs. In the case where it is not possible to define an AE as treatment emergent or not, the AE will be classified by the worst case; i.e. treatment emergent.

AEs will be coded using the MedDRA dictionary, version 23.0.

An overall summary of number and percentage of subjects within each of the categories described in the sub-sections below will be provided by treatment group based on the SAF analysis set. Should a subject experience multiple event within a category, the subject will be counted only once for that category.

All AEs (prior and TEAE) will be listed.

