- Shift from baseline to the worst post-baseline observed value during D1-D14 according to the DAIDS toxicity grades (for quantitative parameters with available DAIDS toxicity grades; refer to [Section 17.3.2](#))
- Listing of subjects with at least one post-baseline laboratory observed value meeting a DAIDS toxicity grade  $\geq 3$  (for quantitative parameters with available DAIDS toxicity grades; refer to [Section 17.3.2](#))
- Shifts from baseline to the maximum/minimum post-baseline observed value during D1-D14 according to normal range criteria (for quantitative parameters without DAIDS toxicity grades; refer to [Section 17.3.3](#));
- Maximum post-baseline ALT/AST observed value categorized as  $< 3 \times$  upper limit of normal (ULN),  $\geq 3$  to  $< 5 \times$  ULN,  $\geq 5$  to  $< 10 \times$  ULN or  $\geq 10$  ULN by maximum post-baseline total bilirubin (TBL) observed value categorized as  $< 2 \times$  ULN or  $\geq 2 \times$  ULN;
- Scatter plots of the maximum post-baseline observed value in ALT value by the maximum post-baseline observed value in TBL value, both expressed as multiple of ULN;
- Scatter plots of the maximum post-baseline observed value in AST value by the maximum post-baseline

Document: \\[REDACTED]\net\enterprise\Apps\sasdata\SASb\SAS\Atea\_Pharmaceuticals\AT-527\ISZA63631\Biostatistics\Documentation\SAP\AT-03A-001\_V1.0\_COVID\_SAP\_PA7.doc

Author: [REDACTED] Version Number: V1.0  
Version Date: 15Apr2021

Template No.: CS\_TP\_BS016 Revision 6

Reference: CS\_WI\_BS005

Effective Date: 02Dec2019

Copyright © 2009, 2010, 2012, 2016, 2018, 2019 [REDACTED] All rights reserved. The contents of this document are confidential and proprietary to [REDACTED] Holdings Inc. and its subsidiaries. Unauthorized use, disclosure or reproduction is strictly prohibited.

observed value in TBL value, both expressed as multiple of ULN;

- A listing of subjects with at least one post-baseline observed ALT value  $> 3 \times \text{ULN}$ , AST value  $> 3 \times \text{ULN}$  or TBL value  $\geq 2 \times \text{ULN}$  will be provided.

All laboratory data will be listed.

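### SAP 17.3 stops both by-arm laboratory shift tables at Day 14, so abnormalities that first appear or worsen later are not tabulated by grade and arm, although the protocol endpoint has no Day 14 end.

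*SAP*

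**What the plan says.** **Endpoint.** Protocol 8.2.5 lists among the safety comparisons "Proportions of subjects experiencing graded laboratory abnormalities". Protocol 8.4 says that "new or worsening laboratory parameters, beginning with or after the first dose of study drug, will be included in the safety analyses". Neither gives a last day.

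**Shift tables.** SAP 17.3 promises, by treatment group, "Shift from baseline to the worst post-baseline observed value during D1-D14 according to the DAIDS toxicity grades" for quantitative parameters that have DAIDS grades. For the others it promises "Shifts from baseline to the maximum/minimum post-baseline observed value during D1-D14 according to normal range criteria".

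**Other outputs in SAP 17.3.** These carry no Day 14 limit:
- values and changes by visit;
- the listing of subjects with a Grade 3 or higher value;
- the table of maximum ALT/AST category by maximum bilirubin category;
- the ALT and AST scatter plots against bilirubin.

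**Visits.** Protocol section 6 states: "Follow-up evaluations will occur at 7 days, 14 days and 49 days after study completion at nominal Day 14". SAP Table B, headed "Analysis visit windows for safety labs and SARS-CoV-2 Test", has rows for Days 21, 28 and 63; the last window is "Day 47 to Day 79".

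**Adverse events.** SAP 17.1 treats an adverse event as treatment-emergent if it started or worsened "on or after the first dose of study drug but no later than 28 days after the last dose of study drug", and adds later events judged possibly related.

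**Change form of 16 March 2022.** It puts the laboratory summary among the items that will not be presented, says that Part B subjects are only listed, and says that the SAP itself will not be revised.

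**The concern.** The DAIDS shift is the only output in SAP 17.3 that crosses laboratory grade with treatment arm for the graded quantitative parameters, so it is the table that delivers the protocol endpoint. Its Day 14 limit narrows that endpoint. A subject whose creatinine first reaches Grade 3 at Day 21 would appear in the Grade 3-or-higher listing, yet would stay in the shift table at the worst grade seen by Day 14, possibly no event at all. By-arm proportions can only be understated in this way, never overstated.

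This matters because protocol 1.4 cites organ toxicity seen with some nucleoside analogues (liver, muscle, heart, nerve, pancreas, kidney) as background to its laboratory monitoring. For CK, creatinine, amylase, lipase and the blood counts, a late change would have no graded comparison between arms.

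**Working it through.** The check is date arithmetic and a comparison of sections. No sample size, power or alpha is involved.

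**1. Follow-up days.** Inputs: 7, 14 and 49 days after Day 14 (protocol section 6).
14 + 7 = 21; 14 + 14 = 28; 14 + 49 = 63. These reproduce the last three target days in SAP Table B.

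**2. Visits covered by the shift tables.** Post-baseline targets in Table B: Days 2, 5, 8, 10, 12, 14, 21, 28, 63, which is 9.
- At or before Day 14: 6 of 9 (67%).
- After Day 14: 3 of 9 (33%), namely Days 21, 28 and 63.

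**3. The adverse event window, for comparison.** Ten doses at 12-hour intervals put the last dose 9 × 12 = 108 hours after the first. Protocol 5.4.2 allows a morning or evening start. Illustrative start times:
- 08:00 start: 8 + 108 = 116 hours from midnight of Day 1, so the last dose is on Day 5; 5 + 28 = Day 33.
- 20:00 start: 20 + 108 = 128 hours, so the last dose is on Day 6; 6 + 28 = Day 34.

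Either way, Days 21 and 28 lie inside the adverse event window and outside the shift tables. Of the 8 Table B targets inside that window, the shift tables cover 6 (75%).

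**4. What happens to a late value under SAP 17.3**

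| Late abnormality (after Day 14) | By-arm count | Other output |
|---|---|---|
| ALT/AST Grade 3-4 | Yes: the category cuts at 5 and 10 × ULN equal the DAIDS Grade 3 and 4 limits in SAP Appendix 4 | Listing, scatter plot |
| ALT/AST Grade 1-2 | Coarse: the band below 3 × ULN mixes no event, Grade 1 (from 1.25) and lower Grade 2 (from 2.5) | By-visit values, full listing |
| Total bilirubin | Coarse: one cut at 2 × ULN, which falls inside Grade 2 (1.6 to <2.6) | By-visit values, listings |
| Other parameters, Grade 3 or higher | Not by grade | Listing; by-visit values where the parameter is summarized |
| Other parameters, Grade 1-2 | Not by grade | By-visit values where summarized; full listing |
| Any abnormality recorded as an adverse event | Yes, in the treatment-emergent tables, as an event | Adverse event listing |

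**5. Boundary.** Table B maps Days 15-18 to the Day 14 visit. SAP 17.3 does not say whether such a value counts as falling within Days 1-14.

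**6. Effect of a longer window.** A cut-off at 28 days after last dose would raise coverage from 6 to 8 of 9 targets, but the Day 28 window (Days 26-46) would straddle the cut-off at Day 33 or 34. Using every post-baseline value gives 9 of 9 and matches protocol 8.4.

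**The case against.** The best defence is that late laboratory data are not lost. SAP 17.3 counts late ALT/AST elevations by arm at the Grade 3 and 4 limits. Protocol 5.6.1 asks for clinically significant Grade 3-4 values to be reported as adverse events, and protocol 7.1 requires this for values needing intervention; those events are then tabulated by arm and severity. By-visit summaries and treatment-ordered listings hold the rest. A 14-day window matches the primary study period. Protocol 8.2.5 prescribes neither a shift table nor its window. Follow-up may be by telephone or video, so few late samples may exist. And the March 2022 form removes laboratory summaries altogether.

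Much of this stands, and it rules out three stronger readings:
- **Late toxicity is never counted by arm.** Not so, for the liver and adverse event routes just given.
- **The SAP contradicts itself because its treatment-emergent window is longer.** That window is defined for adverse events, not laboratory values. Different windows are a choice, though an awkward one.
- **The tables cover only 14/33 = 42% of the relevant period.** That ratio counts calendar days. Laboratory values come from visits, and 6 of 9 visits are covered.

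What does not stand is that the other outputs replace the graded table. By-visit summaries of quantitative values give means and medians, not proportions by grade. Protocol 7.1 keeps abnormalities without clinical significance out of the adverse event record, and lets an event's grade differ from the laboratory grade. The change form limits the practical effect of the Day 14 rule, but it does not align SAP 17.3 with the protocol endpoint.

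**Conclusion.** The point holds in a limited form and is minor. SAP 17.3 restricts the only grade-by-arm table to Days 1-14. The protocol endpoint has no such end, and the Grade 3-or-higher listing and ALT/AST maxima in the same section use any post-baseline value. Three of nine planned post-baseline laboratory windows are left out. The gap is widest for parameters other than ALT, AST and bilirubin, where late Grade 3 or higher values are only listed and late Grades 1-2 appear only as values.

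The number of events affected cannot be derived from the documents. The conclusion assumes that some laboratory samples are taken after Day 14. That rests on Table B, which also serves to map visits labelled unscheduled; the safety-laboratory row of protocol Table 6-1 is not legible enough in the available text to confirm it. If follow-up is largely remote, few values would change.

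A reader might infer that the Day 14 limit is why the final outputs lack a by-arm laboratory comparison. The documents do not support that: the March 2022 form drops the laboratory summary for a separate reason, the early end of the study and the reuse of the interim outputs.

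**What to change.** In SAP 17.3:
1. Run both shift tables (DAIDS grade and normal range) on all post-baseline values after first dose, scheduled and unscheduled.
2. Keep Days 1-14 as a second panel for the treatment and early post-treatment period.
3. State that values from Days 15-18 mapped to the Day 14 visit count in the Days 1-14 panel.

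In the March 2022 change form, keep the graded shift table among the outputs; otherwise the endpoint is not reported by arm whatever its window. The form only lists Part B subjects, so unless that also changes the table would cover Part A alone.

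The cost is a change of wording, one program filter and one extra panel, with no new data and no change to visits or treatment. The drawback is that late values are more open to causes other than study drug. That applies equally to both arms, and the second panel keeps the early picture separate.

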### 17.3.1. LABORATORY STANDARDIZATION

As laboratory parameters are collected locally and have different normal ranges in the database, observed values of all subjects will first be standardized to a unique set of normal range using the location-scale standardization formula (Chuang-Stein, 1992):

$$\bullet \quad s = L_S + (x - L_X) \frac{(U_S - L_S)}{(U_X - U_X)}$$

where:

- o  $s$  = standardized observed value;
- o  $x$  = original observed value;
- o  $L_s$  = Lower Limit of the normal range chosen to be the standard normal range;
- o  $U_s$  = Upper Limit of the normal range chosen to be the standard normal range;
- o  $L_x$  = Lower Limit of the normal range associated with the original observed value;
- o  $U_x$  = Upper Limit of the normal range associated with the original observed value;

It is to be noted that the choice of the standard normal range is arbitrary.

Standardized values will be used for all analyses and ranges/ DAIDS toxicity grades.

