### 17.3. LABORATORY EVALUATIONS (INCL. BLOOD GAS AND COAGULATION)

A serum pregnancy test will be performed at the screening visit, and urine or serum pregnancy test will be performed on Day 1 prior to the first dose and at hospital discharge or early termination. Chemistry (incl. blood gas,

Document: \[REDACTED]\net\enterprise\Apps\sasdata\SASb\SAS\Atea\_Pharmaceuticals\AT-527\SAZ\A63631\Biostatistics\Documentation\SAP\AT-03A-001\_V1.0\_COVID\_SAP\_PA7.doc  
Author: \[REDACTED] Version Number: V1.0  
Template No.: CS\_TP\_BS016 Revision 6 Version Date: 15Apr2021  
Effective Date: 02Dec2019 Reference: CS\_WI\_BS005

Copyright © 2009, 2010, 2012, 2016, 2018, 2019 \[REDACTED] All rights reserved. The contents of this document are confidential and proprietary to \[REDACTED] Holdings Inc. and its subsidiaries. Unauthorized use, disclosure or reproduction is strictly prohibited.

COVID-19 Statistical Analysis Plan

ATEA Pharmaceuticals  
Protocol AT-03A-001  
Page 50 of 77

cardiac related tests), hematology, coagulation and urinalysis will be performed as per the schedule of events (refer to protocol, Section 6.5). A list of laboratory parameters to be included in the outputs is included in [APPENDIX 3](#).

Quantitative laboratory parameters reported as “< X”, i.e. below the lower limit of quantification (BLQ) or “> X”, i.e. above the upper limit of quantification (ULQ), will be converted to X for the purpose of quantitative summaries, but will be presented as recorded, i.e. as “< X” or “> X” in the listings. Observed values will then be standardized (refer to [Section 17.3.1](#)) before being summarized and changes from baseline will be computed based on the standardized observed values.

The parameters which need clinical assessment will only be listed (Direct Bilirubin).

For hematology, only the following key parameters will be summarized: hemoglobin, hematocrit, RBC, platelets, WBC, neutrophils.

The following summaries will be provided by treatment group based on the SAF analysis set for each of chemistry, hematology, coagulation, and urinalysis laboratory parameters:

- Observed and change from baseline in Standard International (SI) units by visit (for quantitative parameters);
- Number and percentage of subjects in each laboratory parameter category by visit (for categorical parameters);

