## COVID-19 Statistical Analysis Plan

DAIDS Term	Laboratory Test	No Event	Grade 1	Grade 2	Grade 3	Grade 4
Creatinine, High	Creatinine ( $\mu$ mol/L)	Criteria for Grade 1 - 4 not met	1.1 to 1.3 x ULN	> 1.3 to 1.8 x ULN OR Increase to 1.3 to < 1.5 x participant's baseline	> 1.8 to < 3.5 x ULN OR Increase to 1.5 to < 2.0 x participant's baseline	$\geq$ 3.5 x ULN OR Increase of $\geq$ 2.0 x participant's baseline
Creatinine Clearance, Low	Creatinine Clearance (mL/s)	Criteria for Grade 2 - 4 not met	NA	< 1.5 to 1 OR 10 to < 30% decrease from participant's baseline	< 1 to 0.5 OR 30 to < 50% decrease from participant's baseline	< 0.5 OR $\geq$ 50% decrease from participant's baseline or dialysis needed *

Document: \\[REDACTED]net\enterprise\Apps\sasdata\SASb\SAS\Atea\_Pharmaceuticals\AT-527\SZA63631\Biostatistics\Documentation\SAP\AT-03A-001\_SAP\_V1.0\_COVID\_SAP\_PA7.doc

Author: [REDACTED]

Version Number: V1.0

Version Date: 15Apr2021

Template No.: CS\_TP\_BS016 Revision 6

Effective Date: 02Dec2019

Reference: CS\_WI\_BS005

Copyright © 2009, 2010, 2012, 2016, 2018, 2019 [REDACTED] All rights reserved. The contents of this document are confidential and proprietary to [REDACTED] Holdings Inc. and its subsidiaries. Unauthorized use, disclosure or reproduction is strictly prohibited.

COVID-19 Statistical Analysis Plan

ATEA Pharmaceuticals  
Protocol AT-03A-001

Page 73 of 77

DAIDS Term	Laboratory Test	No Event	Grade 1	Grade 2	Grade 3	Grade 4
Cardiac Troponin I, High	Troponin I (ng/L)	Criteria for Grade 4 not met	NA	NA	NA	Levels consistent with myocardial infarction or unstable angina as defined by the local laboratory *
Glucose Fasting, High	Glucose (mmol/L)	< 6.11	6.11 to < 6.95	6.95 to < 13.89	13.89 to < 27.75	≥ 27.75
Glucose, Low	Glucose (mmol/L)	≥ 3.55	3.05 to < 3.55	2.22 to < 3.05	1.67 to < 2.22	< 1.67
Cholesterol Fasting, High	Total cholesterol (mmol/L)	< 5.18	5.18 to < 6.19	6.19 to < 7.77	≥ 7.77	NA
Triglycerides Fasting, High	Triglycerides (mmol/L)	< 1.71	1.71 to 3.42	>3.42 to 5.7	>5.7 to 11.4	> 11.4
Creatine Kinase, High	Creatine kinase (IU/L)	< 3 x ULN	3 to < 6 x ULN	6 to < 10x ULN	10 to < 20 x ULN	≥ 20 x ULN

Document: \\[REDACTED]\net\enterprise\Apps\sasdata\SASb\SAS\Atea\_Pharmaceuticals\AT-527\SZA63631\Biostatistics\Documentation\SAP\AT-03A-001\_SAP\_V1.0\_COVID\_SAP\_PA7.doc

Author: [REDACTED]

Version Number: V1.0

Version Date: 15Apr2021

Template No.: CS\_TP\_BS016 Revision 6

Effective Date: 02Dec2019

Reference: CS\_WI\_BS005

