## COVID-19 Statistical Analysis Plan

DAIDS Term	Laboratory Test	No Event	Grade 1	Grade 2	Grade 3	Grade 4
Hemoglobin, Low	Hemoglobin (g/L)	Male: $\geq 109$ ; Female: $\geq 104$	Male: 100 to 109; Female: 95 to 104	Male: 90 to < 100; Female: 85 to < 95	Male: 70 to < 90; Female: 65 to < 85	Male: < 70; Female: < 65
WBC, Decreased	White blood cell count total (x10E9/L)	> 2.499	2.000 to 2.499	1.500 to 1.999	1.000 to 1.499	< 1.000
Absolute Neutrophil Count, Low	Absolute neutrophils count (x10E9/L)	> 1.000	0.800 to 1.000	0.600 to 0.799	0.400 to 0.599	< 0.400
Absolute Lymphocyte Count, Low	Absolute lymphocyte count (x10E9/L)	$\geq 0.650$	0.600 to < 0.650	0.500 to < 0.600	0.350 to < 0.500	< 0.350
Platelets, Decreased	Platelet count (x10E9/L)	$\geq 125.000$	100.000 to < 125.000	50.000 to < 100.000	25.000 to < 50.000	< 25.000

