## Changes to Planned Statistical Analyses Form

Page 2 of 3

Customer:	ATEA Pharmaceuticals
Protocol No.:	AT-03A-001
Project Code:	SZA63631
Date (DDMMYYYY):	16Mar2022

- PRI sensitivity analysis (except on mITT analysis set).
- PRI supplementary analysis (except on subgroups).
- Proportion of subjects with respiratory failure or death (RFD) by Day 28.
- Sensitivity analyses for key secondary efficacy endpoints.
- Proportion of subjects improving/worsening from baseline in clinical status.
- All-cause mortality.
- Duration of hospitalization.
- Time to first SARS-CoV-2 Negative Test.
- Proportion of subjects SARS-CoV-2 positive at each time point.
- Sensitivity analysis for time to clinical recovery by day 14.
- All other secondary efficacy analysis.
- All exploratory analysis except level of SARS-CoV-2 infection virus titer over time and time-weighted average change from baseline in quantitative SARS-CoV-2.
- Treatment emergent adverse events by relationship to study treatment summary.
- Treatment emergent adverse events by relationship to non-study treatment summary.
- Treatment emergent adverse events leading to discontinuation from study summary.
- Death summary.
- Laboratory evaluations summary.
- Vital signs summary.
- ECG summary.
- Physical examination summary.

- The study is conducted in 2 Parts. Part A evaluates an AT-527 dose of 550 mg BID for 5 days and Part B evaluates a dose of 1100 mg BID for 5 days. Part B patients will only be listed.

Describe the process used to decide on the change(s) and who was involved:

While creating the shells and working on the Interim Analysis (IA) outputs it appeared some updates were needed. As the study is terminating early, the IA tables/figures outputs will be used for the final delivery. Atea and [REDACTED] biostatistical teams were involved.

The group(s) responsible for the change(s) and implications for the study:

[REDACTED] Biostatistical team will deliver the datasets and outputs according to these updates. The SAP will not be updated.

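### DAIDS laboratory grades are derived from values rescaled to an arbitrarily chosen reference range, so grades can shift, chiefly for tests with fixed cut-offs

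*SAP*

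**What the plan says.** SAP 17.3.1 explains that laboratory tests are run locally with differing normal ranges. It converts all results to a single range by a location-scale formula. No target range is specified: "It is to be noted that the choice of the standard normal range is arbitrary". The section ends: "Standardized values will be used for all analyses and ranges/ DAIDS toxicity grades". SAP 17.3 adds that "changes from baseline will be computed based on the standardized observed values".

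SAP Appendix 4 defines the grades in three ways:

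- **Fixed concentrations or counts**, for example sodium, potassium, platelets and hemoglobin (grade 3 is "Male: 70 to < 90; Female: 65 to < 85" g/L).
- **Multiples of the ULN**, for example ALT, AST and bilirubin.
- **Change relative to the subject's own baseline**, as one route to a creatinine or creatinine clearance grade (creatinine grade 3 includes "Increase to 1.5 to < 2.0 x" baseline).

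The outputs in SAP 17.3 that use these quantities include a DAIDS shift table, ALT/AST-by-bilirubin displays, a liver-test listing, and this listing for grade 3 or higher: "Listing of subjects with at least one post-baseline laboratory observed value meeting a DAIDS toxicity grade".

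Protocol 8.2.5 makes the proportion of subjects with graded laboratory abnormalities a safety endpoint, "With abnormality grades defined in the referenced DAIDS table". It does not mention rescaling, and neither does the list of changes in SAP 3.3 as supplied. The change form of 16 March 2022 includes "Laboratory evaluations summary" among the items not presented and does not alter 17.3.1.

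**The concern.** Location-scale standardization is reasonable for pooling continuous results from laboratories with different ranges. It does not suit grading. A fixed cut-off such as 125 mmol/L for sodium applies to the measured concentration; once the result has been shifted and stretched to another range, the comparison no longer means what the DAIDS table intends. A linear map with a non-zero intercept also fails to preserve ratios, so multiples of ULN and of baseline can change.

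The same blood result could then be graded differently depending on which range the programmer picks. Errors can go both ways: a severe value can drop out of the grade 3 or higher listing, and a milder one can enter it.

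**Working it through.** **Inputs.** The formula is from SAP 17.3.1 and the cut-offs are from SAP Appendix 4. The plan states no figure to reproduce. The documents give no local or standard reference ranges, so **every range below is an assumption**.

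**Formula.** With local limits Lx, Ux and chosen limits Ls, Us:

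s = Ls + (x − Lx)(Us − Ls)/(Ux − Lx)

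The denominator appears in the text as Ux − Ux, which is zero. I read it as Ux − Lx; it should be checked against the source PDF.

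**What the map preserves.** Lx maps to Ls and Ux to Us, so low/normal/high flags never change. For a ULN multiple m = x/Ux,

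s/Us = 1 + (m − 1)(1 − Ls/Us)/(1 − Lx/Ux),

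so above the ULN the multiple is kept only when Lx/Ux = Ls/Us, for example when both lower limits are 0. If the ranges coincide, nothing changes.

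**Fixed cut-offs.**

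| Result | Local → chosen range | Rescaled value | Grade |
|---|---|---|---|
| Sodium 124 mmol/L | 135-145 → 136-146 | 136 + (124 − 135)×10/10 = 125 | 3 → 2 |
| Sodium 126 mmol/L | 136-145 → 133-146 | 133 + (126 − 136)×13/9 = 118.6 | 2 → 4 |
| Potassium 6.4 mmol/L | 3.5-5.1 → 3.5-5.3 | 3.5 + 2.9×1.8/1.6 = 6.76 | 2 → 3 |
| Male hemoglobin 85 g/L | 130-170 → 135-175 | 135 + (85 − 130)×40/40 = 90 | 3 → 2 |
| Male hemoglobin 85 g/L | 120-160 → 135-175 | 135 + (85 − 120)×40/40 = 100 | 3 → 1 |
| Platelets 55 ×10⁹/L | 150-400 → 150-450 | 150 + (55 − 150)×300/250 = 36 | 2 → 3 |
| Platelets 20 ×10⁹/L | 150-400 → 150-450 | 150 + (20 − 150)×300/250 = −6 | impossible value |

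**Ratio to baseline.** Creatinine rises from 70 to 100 µmol/L, a ratio of 100/70 = 1.43 (grade 2). Moving 60-110 to 44-97 gives 44 + 10×53/50 = 54.6 and 44 + 40×53/50 = 86.4. The ratio becomes 86.4/54.6 = 1.58 (grade 3), although both samples come from the same laboratory.

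**ULN multiples.**

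- ALT 216, 0-40 → 10-50: 216/40 = 5.4 × ULN becomes 226/50 = 4.52 × ULN, grade 3 → 2.
- ALT 128, same ranges: 3.2 × ULN becomes 138/50 = 2.76 × ULN, below the listing threshold of more than 3 × ULN.
- Bilirubin 43, 0-21 → 3-21: 43/21 = 2.05 × ULN becomes (3 + 43×18/21)/21 = 39.9/21 = 1.90 × ULN, below the listing threshold of 2 × ULN.

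**Which tests are most exposed.** I took all ordered pairs of five or six assumed ranges per test over a grid of abnormal results. The derived grade changed at these shares of grid points:

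- Fixed cut-offs: potassium 59%, sodium 44%, male hemoglobin 57%, platelets 51%.
- ULN-based: ALT 18%, bilirubin 7%, never by more than one grade.

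For the fixed cut-offs, shifts of two grades were at most about 7% of grid points. A second set of assumed ranges, each mapped to one standard range, gave potassium 57%, sodium 44%, hemoglobin 65%, platelets 44% and ALT 10%, with ALT at 0% when both lower limits are 0. These are shares of an assumed grid, not patient rates.

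**The case against.** **The March 2022 form may already remove the affected outputs.** SAP 17.3 introduces the tables, plots and listings together as summaries, and the form drops the laboratory evaluations summary. On that reading nothing affected reaches the final report. This limits the practical impact, but it is not settled by the text. The form names no laboratory listing as dropped, leaves 17.3.1 in force, and says that Part B subjects will only be listed. For the higher-dose cohort, listings are therefore what matters.

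**The liver listing may use original values.** SAP 17.3 refers there to observed values, and 17.3.1 distinguishes original from standardized observed values. The two liver-listing examples above therefore depend on reading the rule for all analyses as covering that listing. The ambiguity is real. The rule for DAIDS grades is explicit.

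**The grid shares depend on the assumed ranges.** This is correct. Dropping the single sodium range 133-146 cuts the sodium share from 44% to 22%, and using only 3.5-5.0 and 3.5-5.1 for potassium gives about a third. Protocol 4.3 excludes male hemoglobin below 12 g/dL and platelets below 80 × 10⁹/L at screening, so the low values used here need a fall after screening. The shares show which tests are most exposed; they do not estimate the error in this trial.

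**No treatment comparison is at risk.** Safety data are not tested, the rescaling ignores treatment arm, and randomization is stratified by region, so misgrading should be similar in both arms. That stands: the expected harm is blurred grades and unreliable listings, not bias toward one arm.

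**Conclusion.** The concern holds. Applied as written, SAP 17.3.1 compares rescaled results with cut-offs that were not rescaled, so a derived grade can be wrong and can depend on an arbitrary choice. In the assumed examples the effect runs from none to two grades, largest for fixed cut-offs and at most one grade for ULN-based tests. The actual size cannot be known without the laboratories' ranges.

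The reach is limited to SAP-derived grades, ULN multiples and baseline ratios. Low/normal/high flags are unaffected, and nothing in the documents applies the rescaling to investigator-reported AE severity or the stopping rules. In the final delivery the main exposure is the grade 3 or higher listing and possibly the liver listing, if they are produced. The rule should be corrected because it bears on a protocol safety endpoint, but it does not threaten the efficacy conclusions.

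**What to change.** Replace the last sentence of SAP 17.3.1 with:

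> DAIDS grades and multiples of ULN are derived from the original reported value in SI units. They use the fixed cut-off, the reporting laboratory's own ULN or LLN, or the subject's own original baseline value, according to the Appendix 4 criterion. Standardized values are used only for pooled by-visit descriptive summaries.

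The change form says that the SAP will not be reissued, so a line on that form is the practical route. It should also state whether the grade 3 or higher and liver listings are produced and on which values. The low/normal/high rule needs no change. The formula's denominator needs only a check against the source PDF.

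The cost is one sentence and a simpler derivation. No new data are needed, because the local values and ranges are already in the database.
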